9.1 Screening Procedures

Eligible patients will be identified from the local trial site's clinical database. These will be given/sent the Patient Information Sheet and invited to contact the trial PI or research nurse at the study site. Information may also be given to eligible patients at

Out-patient and Day Care visits and on recovery from acute episodes of SCD when awaiting discharge from hospital. Eligible patients will have the opportunity to discuss the trial and ask questions with investigators and trial nurses.

9.2 Informed Consent

It is the responsibility of the Investigator, or appropriately GCP trained person delegated by the Investigator as documented in the site delegation log, to obtain written informed consent from each subject prior to any participation/ study specific procedures. This should follow adequate explanation of the aims, methods, anticipated benefits and potential hazards of the study. If the participant wishes to speak to a physician (Sub-Investigator or Chief Investigator) who is present or contactable via telephone, further information can be given to the participant and any questions can be answered immediately.

Consent may be obtained by a delegated medically trained member of the research team or a delegated research nurse (any research nurse delegated to take consent will be trained in consent and have a specialised knowledge in Sickle Cell Disease). The names of all individuals entitled to obtain consent will be recorded in the delegation log.

If the research nurse has taken consent, the PI or trial physician (co-Investigator) will counter sign the consent form and document acknowledgment within the patient's notes before treatment is given. This counter signature and acknowledgment process is used where the participant is content with the information and discussions with the research nurse. In counter signing the consent form and documenting in the patient's notes prior to treatment, the physician indicates that he/she has oversight of the participant's case and planned treatment.

If for some reason, a physician (Sub-Investigator) is not accessible in person or by phone and the participant wishes to speak with them, a second consent visit should be arranged and the research nurse will not take consent at this time. As stipulated by GCP, the patient should be given ample time to consider giving their consent for the study. It is felt that 24 hours gives sufficient time for the patient to consider their participation within the study and give informed consent. The date that the Patient Information Sheet (PIS) is given to the patient must be documented within the patient's notes to ensure that sufficient time is given (minimum 24 hours).

The Investigator (or other qualified person) must explain to the potential participant that they are free to refuse any involvement within the study or alternatively withdraw their consent at any point during the study and for any reason.

If there is any further safety information which may result in significant changes in the risk/benefit analysis, the PIS and Informed Consent Form (ICF) will be reviewed and updated accordingly. All subjects that are actively enrolled on the study will be informed of the updated information and given a revised copy of the PIS/ICF in order to confirm their wish to continue on the study.

9.3 Consent process

The consent process involves three procedures:

- 1. Consent
- 2. Checking of continued consent
- 3. Confirmation of consent

9.3.1 Consent

Consent will be obtained when the subject is healthy, prior to presenting with APC (Appendix 1). Consent can be obtained in any appropriate outpatient setting at the participating trial centre. Most patients will be identified during their routine haemoglobinopathy clinic appointment. Consenting patients will sign the study Consent Form. Copies of the consent form will be held by the patient, scanned onto the electronic patient record (EPR) or paper notes, and held in a secure file in the Trial Office. Patients will be given a personalised Trial Card. The name, date of birth, and hospital number and consent status will be maintained on the Enrolment Log.

9.3.2 Checking of continued consent

Presentation with APC after being consented will depend on clinical circumstances and may not occur for many months. During this time, their eligibility may have changed, or they may decide they no longer wish to take part in the trial. It is therefore necessary to confirm continued eligibility and agreement to participate for the duration of the trial.

To achieve this, consented patients will be contacted at six months (with an allowed flexibility of one month before or three months after), and six-monthly thereafter (with an allowed flexibility of one month before or three months after) in order to check against eligibility criteria and repeat verbal consent. This will be done by phone call or direct contact with the patient, and undertaken by a delegated member, who will sign and date the Consent Form for each episode of confirmation.

The updated form will replace the previous form, and sent to the patient, scanned onto the EPR and held in the trial file. Checking of consent will be recorded on the Enrolment Log and medical notes. If the re-checking of eligibility and consent is not done within the allowed time interval, the patient will be withdrawn from the study. A patient may be re-entered, but would need to be re-consented as a new patient.

9.3.3 Confirmation of consent (See Trial flow charts, 2 and 3)

Consented subjects will be instructed to call their local trial centre if they have APC and feel they need treatment in hospital. During this phone call with the local trial centre nurse, the following procedures will be done;

- 1. Verbal confirmation of consent and checking trial registration number
- 2. Confirming eligibility of APC using APC triage algorithm
- 3. Confirming trial eligibility against inclusion and exclusion criteria

Provided that eligibility criteria are met, the patient will be informed that they meet trial entry criteria, and will be randomized (See section 9.4).

9.3.4 Personnel taking consent

All consent and assent procedures must be done by personnel who are GCP trained, and who have undertaken trial training (recorded in the training log). Delegation for consent and assent will be recorded on the delegation log.

9.4 Randomization (See trial flow chart, Appendix, part 2 and 3)

Randomization will be done over the phone when a pre-consented subject calls the local trial centre with symptoms of APC. The procedures to be done by the trial nurse at the local trial centre to confirm consent and eligibility are listed in Section 9.2.3.

- 1. Verbal confirmation of consent and checking trial registration number
- 2. Confirming eligibility of APC using APC triage algorithm
- 3. Confirming trial eligibility against inclusion and exclusion criteria

If eligible for randomization, the local trial centre will next confirm the following

- 1. Both ED and ACU are available and resourced for treating the trial patient
- 2. Timing will permit 6 hours of treatment on ACU.

Once these items have been confirmed, randomization will be carried out by the local clinical trial nurse using a Queen Mary University of London Pragmatic Clinical Trials Unit dedicated online randomisation system. Participants will be randomised in a 1:1 ratio to the ambulatory care unit or hospital emergency department, stratifying by recruiting site, previous history of APC and age.

9.5 Schedule of Treatment

Routine management of APC and of complications of APC should follow standard of care at the local trial centre. This includes selection of analgesic drugs, doses and route of administration, non-opioid analgesia and non-pharmacological treatments to manage pain. Care during the APC will be given by the standard care team rather than the trial team.

9.6 Schedule of Assessment

See Table 1.

Study event	Screening	Consent and enrollment	Phone triage with APC	ED or ACU with APC	Discharge	Follow up	Follow up						
Study Day			1		1							1.1 douro	20. devie
Study event number	4				1	1	-			10	14	14 days	26 days
	1	4	2 3	4	5	6				10	11	12	13
Study time (nours)				(1	2	: 3	4	+ t	6			
Eligibility	X												
Confirm individual protocol		х	х	х									1
Given patient information sheet	х												1
Informed consent		х											1
Confirm consent			Х										
Demographics ^b		Х											
Medical history ^c		Х	Х										
Confirm inclusion/exclusion criteria			Х										
Confirm eligible APC			Х										
Confirm ED and ACU care available			Х										
Randomisation			Х										
Concomitant medication ^d		Х	Х										
Social determinants of health assessment		Х	Х								Х	Х	Х
EQ-5D-5L °		Х	Х								Х	Х	Х
Satisfaction with care questionnaire ^f		Х									Х	Х	Х
Vital signs ^g				Х	Х	Х	Х	Х	Х	Х	Х		
Pain score ^h				Х	Х	Х	Х	Х	Х	Х	Х	Х	Х
Protocol adherence ⁱ											Х		
Time to. disposition ^j											Х		
Time to readiness for discharge											Х		
Cumulative opiate dose k											Х		
Resource use CRF including Work Productivity and Activity Impairment Questionnaire ^m	r	х									х	x	х
APC episode resource use CRF											Х	Х	Х
Adverse events ⁿ											Х	Х	Х
Length of stay											Х		
Re-attendance												Х	Х
EQ-5D-5L for care givers		Х										Х	Х
Care giver questionnaire including Work Productivity and Activity Impairment Questionnaire		x										x	х

Abbreviations: ED; emergency department, ACU; ambulatory care unit, APC; acute painful crisis.

^a 6 hours, or until discharge if before

^b Age, sex, genotype

^cPast medical history, to include sickle complications

^d Collect information from the paper or electronic drug chart

^e Provide patient with the EQ-5D-5L questionnaire. To complete on presentation and 7 days after presentation.

^f Patient satisfaction questionnaire

^g Hourly for the first 6 hours a per standard of care. These results should be taken from the hospital paper or electronic record. Record actual values and percentage of scheduled measurement

^{*h*} Visual pain score to be taken by dedicated trial team. Score to be taken at baseline and hourly for the first 6 hours

^{*i*} Use the hospital or paper record to confirm adherence to protocol

^{*j*} Was the patient admitted or discharged from ED or ACU

^{*k*} Cumulative opioid dose over the first 6 hours. Use data from the hospital paper or electronic drug chart.

¹To include, but not limited to; acute chest syndrome, hospital acquired pneumonia, any other significant adverse event CTCAE grade > 3

^m Work Productivity and Activity Impairment Questionnaire

 $^{\it n}$ Record any AEs or SAEs in the 7 days from presentation. Use patient's notes and discharge summary.

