6.3 Primary endpoint

• Reduction in pain score during the first 6 hours after presentation to ED and ACU using a 0-10 numeric rating scale.

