6.4 Secondary endpoints

- Time to first analgesia, defined as time from presentation in ACU or ED to first dose of opioid analgesia administered. (For subjects given parenteral opioid prior to arrival in care unit, e.g. in ambulance, timing will start from one hour after parenteral analgesia given in ambulance, even if subject presents less than one hour after analgesia given in ambulance)
- Adherence to NICE guideline in safety observations (defined as proportion of hourly safety observations (respiratory rate, sedation score) taken within first 6 hours (+/- 30 mins)
- Adherence to care plan in analgesia doses (defined as proportion of analgesia doses given according to protocol within first 6 hours (+/- 30 minutes)
- Fit for discharge by 6 hours after first analgesia (defined as pain score 5 or less for at least 2 consecutive hourly assessments; no requirement for parenteral opioid for at least 2 hours and acceptable oral analgesia protocol available for use at home, NEWS score green for >2 hours, patient able to self-administer oral medication, patient mobile. All the above assessed by physician and agreed with patient)
- Time from first analgesia to fit for discharge (defined as pain score 5 or less for at least 2 consecutive assessments; no requirement for parenteral opioid for at least 2 hours and acceptable oral analgesia protocol available for use at home, NEWS score green for >2 hours, patient able to self-administer oral medication, patient mobile. All the above assessed by physician and patient).
- Cumulative dose of morphine or equivalent opioids in first 6 hours and first 24 hours
- Proportion admitted to hospital from ACU or ED
- Length of hospital stay (for those admitted to hospital), length of hospital stay Patient satisfaction with care assessed using SCAPE questionnaire 14 and 28 days after discharge
- Health economic analyses of comparative patient health-related quality of life, costs and cost-effectiveness of ACU versus ED care from the perspective/s of health and social care (NHS and PSS) and, separately, wider society
 - Costs at 28 days post-randomisation
 - QALY at 28 days post-randomisation
 - Incremental cost-effectiveness ratio

7. Study population

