9.10 Data Collection and Follow up for Withdrawn Subjects

A first APC treated in on trial can be used for data analysis if a patient subsequently withdraws consent from continuing in the trial for a second episode.

10. Assessment and management of risk

No investigational medicinal product is being used in this trial. The analgesic drugs and any non-pharmacological agents used to treat pain will be the same as in their standard care protocol. Observations and any bloods tests or diagnostic imaging will be performed as required for standard of care, and will not be part of the trial evaluation. Subjects who would normally access ACU for their care may be randomised to ED care, and this may be perceived by the subject as a worse option. The risks for subjects involved in the study include:

- Trial procedures delaying access to standard care.
- Trial procedures interfering with standard care and with teams implementing. standard protocols in acute care and, for those admitted to hospital, after admission to medical wards.
- Patients being discharged from hospital and not followed up according to standard care protocols once discharged.

In mitigation, both treatment arms incorporate measures to improve on current standard of care during the initial stages of hospital management of acute pain. These include allocation of individualised care plans in both arms of the study (treatment in ED or on ACU), enhanced supervision of the trial subjects, which is anticipated to improve patient safety and satisfaction and reduce harm. Prior to implementation of the trial in trial centres, and during the trial implementation period, there will be regular

training sessions for clinical trial staff and standard care staff, to ensure that trial procedures are correctly implemented.

There will also be an independent trial monitoring committee which will evaluate safety and operational problems during the entire clinical trial implementation period.

11. Statistical considerations

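### AE recording starts at presentation although randomisation comes earlier, by phone, so events before arrival and in patients who never arrive fall outside the stated window

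*Protocol*

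**What the plan says.** Protocol Section 9.4 places randomisation before arrival: "Randomization will be done over the phone when a pre-consented subject calls the local trial centre with symptoms of APC". The nurse first confirms consent, applies the triage algorithm, checks eligibility and checks that both units can take the patient. The patient then learns the allocation and is asked to attend that unit (Section 8).

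Section 10 puts this first in its list of risks: "Trial procedures delaying access to standard care". Of patients who would normally use the ACU but are allocated to ED, it says that "this may be perceived by the subject as a worse option".

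The main clocks start on arrival:

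- AEs and SAEs (Section 9.6, Table 1, footnote n): "Record any AEs or SAEs in the 7 days from presentation". The named sources are the patient's notes and the discharge summary.
- Time to first analgesia (Section 6.4): "defined as time from presentation in ACU or ED to first dose of opioid analgesia administered". One exception applies after a parenteral opioid in the ambulance: "timing will start from one hour after parenteral analgesia given in ambulance".
- Primary endpoint (Section 6.3): "Reduction in pain score during the first 6 hours after presentation to ED and ACU".

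Section 11.2 promises an intention-to-treat analysis of everyone as randomised.

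**The concern.** Randomisation is the point from which the arms are comparable and from which the trial answers for what happens. Here it comes before the start of safety recording, and the gap contains the risk that the protocol lists first. Read literally, footnote n leaves out a patient who deteriorates on the way in. It also leaves out a patient who hears the allocation and does not attend, because without a presentation the window never opens.

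The loss need not be balanced. Section 10 expects some patients to see ED as the poorer option. The background in Section 5.1 reports that investigators of a US cohort thought randomisation unworkable, partly because patients would resist allocation to ED alone. If late arrival or non-arrival is commoner in the ED arm, events would be missed more often there, and the AE comparison would no longer match the randomised groups. The external monitoring committee would also have no specified figure for whether access is slower in one arm.

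**Working it through.** **Step 1. Order of events** (Sections 8, 9.3.3, 9.4): call, then checks, then online randomisation, then travel, then presentation. So T(call) < T(randomisation) < T(presentation).

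**Step 2. Which clock each item uses**

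| Item | Place in protocol | Starts at | Before arrival? | Non-arrivers? |
|---|---|---|---|---|
| AE/SAE recording | 9.6, footnote n | Presentation, 7 days | No | No |
| Pain scores | 6.3, 8 | Presentation | No | No |
| Time to first analgesia | 6.4 | Presentation, or one hour after an ambulance dose | No | No |
| EQ-5D follow-up | 8 | Presentation | No | No defined origin |
| Resource-use form | 11.3.2(c) | Randomisation | Incidentally | Incidentally |
| Costs, QALYs | 6.4 | Randomisation | Economic only | Economic only |
| Travel and access time | 11.3.2(c) | No origin stated; for costing | Duration only | No |
| Linked hospital data | 11.3.2(b) | 28 days before the index episode and 28 days of follow-up | Hospital contacts only | Hospital contacts only |
| SAE reporting | 17.5 | No start stated | If staff learn of it | If staff learn of it |
| AE definition | 17.1 | Linked in time to study activities | Yes, by definition | Yes, by definition |

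The ambulance exception does not close the gap. It ties the analgesia clock to the ambulance dose, not to the call or to randomisation.

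**Step 3. Apply the rules to two cases.**

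- *Randomised to ED, stays at home, becomes seriously ill.* Footnote n has no day 0, so nothing is recorded under it. Sections 17.1 and 17.5 make the event reportable if the team hears of it. The rules give different answers.
- *Deteriorates on the way and then arrives.* The onset precedes footnote n's window. Section 7.2 also allows a complication to be found on arrival as an exclusion, which is after randomisation. The protocol does not say whether such a complication then counts as an event.

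**Step 4. Can the delay be derived?** For patients who arrive, probably yes. I assume that the online system stamps the randomisation time. The arrival time is needed as zero for the hourly scores and the analgesia endpoint. Then:

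- randomisation-to-arrival = T(presentation) − T(randomisation);
- randomisation-to-first-opioid = T(first opioid) − T(randomisation).

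Call time is not a listed item. Non-arrivers have no T(presentation), so only their arrival status can be reported, and no item for that is listed.

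**Step 5. Scale.** The plan's 114 per group reproduces: adjusted SD = 3.2 × √(1 − 0.5²) = 2.771; the t-test needs 96.47 per group for a difference of 1.3 at 90% power and two-sided 0.05; 96.47 / 0.85 = 113.5, rounded up to 114. This serves only as a denominator. With an assumed 5–10% non-arrival in one arm, 114 × 0.05 = 5.7 and 114 × 0.10 = 11.4, or about 6 to 11 episodes. The planned 15% loss by 6 hours does not separate out loss before arrival, so it gives no rate to use here.

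**The case against.** A reader might infer that the interval is never measured, that nothing triggers follow-up of a non-arriver, or that such patients have no safety follow-up at all. The protocol does not support any of these readings. Resource use is collected at 14 and 28 days from randomisation. Section 9.7 keeps the study open for 28-day data on all randomised episodes, within the 36-month limit. Linked hospital data could show attendance elsewhere. Section 17.5 requires all SAEs to be reported without limiting them to the time after arrival. The interval itself can probably be derived for patients who arrive.

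Other points on that side are also fair:

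- Presentation is a proper origin for endpoints that compare what two care settings do.
- The external committee's remit in Section 19 covers adverse events and operational problems, and the trial team confirms attendance at the allocated location, so non-arrival would probably be noticed.
- More non-arrival in the ED arm is an inference from a remark about perception. Patients consent in advance, when well, and reconfirm by phone.
- Much of the interval may be travel that the patient would make anyway, so its length does not measure delay caused by the trial.
- The appendix flow charts are only partly legible, and the SAE reporting plan listed in Section 14.1 is not available. Either may cover non-arrival.

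What these points do not remove is the literal rule in footnote n. The other routes are economic data, or depend on someone becoming aware of an event. None is defined as a safety measure or specified for comparison by arm. A later analysis plan could add a report, but it cannot recover events that were not recorded.

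**Conclusion.** The point holds in limited form. The stated AE/SAE window opens later than randomisation and does not open for patients who never arrive. Events there are caught only incidentally, and footnote n does not agree with Sections 17.1 and 17.5 on where recording starts. The risk that Section 10 names first has no specified measure by arm for the external committee.

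The size is unknown. The protocol gives neither the non-arrival rate nor the length of the interval. The 6 to 11 episodes rest wholly on the assumed 5–10% and would be episodes outside footnote n's window, not episodes without any follow-up. An imbalance between arms is plausible from the protocol's own remarks but not shown. The sample size and the presentation-based endpoints are unaffected. This is an inexpensive improvement to data collection that should be made.

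**What to change.** - In Table 1, footnote n, and in Section 17, start AE/SAE recording at randomisation, and reconcile the wording with the AE definition in 17.1 and the SAE rule in 17.5.
- Record call time and arrival time, and keep the randomisation time-stamp with them.
- Report arrival status, randomisation-to-arrival and randomisation-to-first-opioid by arm to the external committee as process-safety measures. These show whether access differs between arms. Call-to-randomisation time is the nearest measure of what the trial's own steps take.
- For randomised patients who do not arrive, count the day-14 and day-28 contacts from randomisation, as resource use already is.
- Leave the pain and time-to-analgesia endpoints on their present clocks.

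The cost is two time fields, some wording, and a few extra items at calls.
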